6.2.2 Follow-up for toxicities

Patients whose treatment is interrupted or permanently discontinued due to an adverse event or clinically significant laboratory value, must be followed up at least once a week (or more frequently if required by institutional practices, or if clinically indicated) for 4 weeks, and subsequently at 4-week intervals, until resolution or stabilization of the event, whichever comes first. Clinical experts or specialists, such as ophthalmologist, endocrinologist, dermatologist, should be consulted as deemed necessary. All patients must be followed up for adverse events and serious adverse events for 30 days following the last dose of BGJ398.

6.2.3 Anticipated risks and safety concerns of the study drug

Eligibility criteria as well as specific dose modification and stopping rules are included in this protocol. Guidelines for prophylactic or supportive treatment for expected toxicities, including management of study-drug induced adverse events, i.e., hyperphosphatemia, and renal toxicities are provided in [Table 6-3](#). Refer to preclinical toxicity and or clinical data found in the [BGJ398 Investigator's Brochure].

6.3 Concomitant medications

The patient must notify the investigational site about any new medications he/she takes after the start of the study drug. All medications (other than study drug) and significant non-drug therapies (including physical therapy, herbal/natural medications and blood transfusions) administered during the study must be listed on the Concomitant Medications. If a drug is listed under "Permitted concomitant therapy requiring caution and/or action" and also under "Prohibited concomitant therapy", the drug should be prohibited.

6.3.1 Permitted concomitant therapy

Any palliative and supportive care for disease related symptoms, including any medication for a concurrent medical condition are permitted, except as specifically prohibited below.

Oral phosphate binders

Phosphate lowering treatment, including a low phosphate diet and phosphate binding therapy, such as sevelamer hydrochloride, should be implemented prophylactically at study drug initiation and modified as clinically indicated throughout BGJ398 administration. Recommendations for treatment are provided in [Table 6-3](#), and should be modified as necessary as per country, package insert or institutional practice.

Hematopoietic growth factors

Hematopoietic growth factors (e.g., erythropoietin, G-colony stimulating factor (CSF) and GM-CSF) are not to be administered prophylactically or to be used to meet eligibility criteria. However, these drugs may be administered per the labeling of these agents or as dictated by local practice or guidelines established by the American Society of Clinical Oncology (ASCO).

Hormone replacement therapies

Hormone replacement therapies such as thyroid and growth hormones are allowed, as well as estrogen replacement hormone treatment.

6.3.2 Permitted concomitant therapy requiring caution and/or action

Drugs that alter the pH of the GI tract

BGJ398 is characterized by pH-dependent solubility, and therefore, medicinal products that alter the pH of the upper gastro-intestinal tract may alter the solubility of both compounds, and limit bioavailability. These agents include, but are not limited to, proton-pump inhibitors (e.g., omeprazole), H₂-antagonists (e.g., ranitidine) and antacids. **Therefore, study drug(s) should be dosed at least 2 hours before or 10 hours after dosing with a gastric protection agent.** Note that some proton-pump inhibitors may inhibit BCRP.

Corticosteroids

Chronic dosing of corticosteroids such as dexamethasone and prednisone is known to induce CYP3A enzymes, thereby increasing the risk of reducing drug exposure to sub-therapeutic levels. In addition BGJ398 is an *in vitro* inhibitor of CYP3A4 and has the potential to increase the systemic exposure of corticosteroids that are metabolized by CYP3A4.

Systemic corticosteroid treatment can be used with caution and minimized to the extent possible.

Substrates and inhibitors

CYP substrates and inhibitors

BGJ398 was shown to inhibit the cytochrome p450 isoenzyme CYP3A4 in *in-vitro* assays, thus, suggesting an increased risk of drug interactions with concomitant medications that are metabolized by CYP3A4. However, such interactions have not been confirmed in patients. Therefore, investigators may administer medications that are known to be metabolized by CYP3A4. Patients must be monitored for potentiation of toxicity and may require dose titration or reduction of the CYP3A4 substrate. In particular caution is advised when substrates with a narrow therapeutic index, such as alfentanil, fentanyl, astemizole, cisapride, diergotamine, ergotamine, pimozone, quinidine, sirolimus, tacrolimus, and terfenadine need to be administered. Please refer to [Appendix 1](#) for the list of medication to be used with caution.

Caution is advised when BGJ398 is co-administered with opioid analgesics. Inhibition of opioid metabolism by CYP3A4 can lead to opioid toxicity, including fatal respiratory depression, or an enhanced risk for QTc prolongation. Patients receiving BGJ398 and opioid analgesics should be carefully monitored. Synthetic opioids with clinically relevant interactions with CYP3A4 inhibitors include, but are not limited to, propoxyphene, fentanyl, alfentanil and sufentanil. Use of alfentanil, a sensitive CYP3A4 substrate with narrow therapeutic window, should be avoided whenever possible. The use of methadone and levomethadyl should also be avoided whenever possible. Refer to the [Appendix 1](#) for the list of medications to be used with caution. Note that the list may not be comprehensive.

Hormonal contraceptives may be affected by cytochrome P450 interactions and are therefore not considered effective for this study. For allowed contraception methods please refer to [Section 5.3](#). Highly effective contraception should be maintained throughout the study.

BGJ398 is a reversible inhibitor of CYP2C8, CYP2C9 and CYP2C19. Permitted medications to be used with caution in this study include those that are sensitive substrates of CYP2C8, CYP2C9, CYP2C19, or those substrates that have a narrow therapeutic index.

BGJ398 is a substrate of CYP3A4. Therefore moderate inhibitors and inducers should be used with caution if no other alternative is available. Strong inhibitors and inducers are prohibited.

Please refer to the [Appendix 1](#) for the list of medications to be used with caution. Please note that the list might not be comprehensive.

Transporter substrates

In vitro data show that BGJ398 is an inhibitor of BCRP. CQM157, a metabolite of BGJ398, is an inhibitor of transporters P-gp, BCRP, OATP1B1, and OATP1B3 (IC₅₀ 2-4 µM). In the absence of data confirming whether transporter interactions occurs *in vivo*, patients receiving medications that are substrate of these transporters must be monitored for potential toxicity and may require dose titration or reduction of the medication.

Non-enzyme inducing Anti-epileptic drugs (non-EIAED)

Non-enzyme inducing anti-epileptic medication (non-EIAED) such as valproic acid, levetiracetam and lamotrigine are allowed with caution. Patients who were previously on a non-EIAED and need to change anti-convulsants, should be started on another non-EIAED if at all possible. EIAEDs are not permitted (see [Section 6.3.3](#) and [Appendix 2](#)).

Anti-emetics

Anti-emetics are allowed for the treatment of nausea or vomiting. It is recommended to avoid using drugs that are known to cause QT prolongation. Note that some anti-emetics have a known risk for Torsade de Pointes, and therefore need to be used with caution. See [Appendix 1](#) for list of drugs that need to be used with caution. Aprepitant is both a sensitive substrate and a moderate CYP3A4 inhibitor and can be used with caution if an alternative is not available.

Possible and conditional risk of QT/QTc interval prolongation or torsade de pointes medications

There is no current evidence that BGJ398 has an effect on cardiac conduction or ECG intervals (see current version of the BGJ398 Investigator Brochure). However, medications that have the potential to prolong the QT/QTc interval or induce torsade de pointe (possible and conditional risk of TdP/QT prolongation) are allowed with caution. Investigators at their discretion may co-administer such medications, but patients should be carefully monitored. See [Appendix 1](#) for list of drugs that need to be used with caution. Please note that the list might not be comprehensive.

6.3.3 Prohibited concomitant therapy

Other investigational and antineoplastic therapies

Other investigational therapies must not be used while the patient is on the study. Anticancer therapy (chemotherapy, biologic and/or radiation therapy other than the study treatments) must not be given to patients while the patient is on the study medication. If such agents are required for a patient then the patient must be discontinued from the study.

CYP inhibitors

Strong inhibitors of CYP3A4 such as the ones listed in [Appendix 2](#) are prohibited because BGJ398 is a likely substrate of this isoenzyme. Caution should be used during administration of moderate inhibitors. The following food products are prohibited: Seville oranges or juice, grapefruit, grapefruit juice, grapefruit hybrids, and pummelos.

CYP inducers

Strong inducers of CYP3A4 are prohibited because their usage would likely decrease the exposure of BGJ398. Therefore, agents such as those listed in [Appendix 2](#) are prohibited. Please note that the list may not be exhaustive.

Phosphorus and calcium

Medications that increase the serum levels of phosphorus and/or calcium are prohibited. These include, but are not limited to, calcium, phosphate, vitamin D, parathyroid hormone (PTH).

Known Risk of QT/QTc interval prolongation or torsade de pointes medications

There is no current evidence that BGJ398 has an effect on cardiac conduction or ECG intervals (See current version of the BGJ398 Investigator Brochure). However, medications that are known to prolong the QT/QTc interval or induce Torsade de Pointes (Risk of TdP/QT prolongation) are prohibited. List of these medications is given in [Appendix 2](#). Please note that the list might not be comprehensive.

Herbal medications
Herbal preparations/medications are not allowed throughout the study. These herbal medications include, but are not limited to: St. John's wort, Kava, ephedra (ma huang), ginkgo biloba, dehydroepiandrosterone (DHEA), yohimbe, saw palmetto, and ginseng. Patients should stop using these herbal medications 7 days prior to first dose of study drug.

Enzyme Inducing Anti-epileptic drugs (EIAEDs)

Enzyme inducing anti-epileptic medication is not allowed (please refer to [Appendix 2](#)). Patients who were previously on a non-EIAED and need to permanently change anticonvulsants, but who cannot change to another non-EIAED must be discussed with Novartis. These patients will be taken off-study unless it is felt that they have benefited from the therapy following discussion with Novartis.

6.4 Patient numbering, treatment assignment or randomization

6.4.1 Patient numbering

Each patient is identified in the study by a Subject Number (Subject No.), that is assigned when the patient is first enrolled for screening and is retained as the primary identifier for the patient throughout his/her entire participation in the trial. The Subject No. consists of the Center Number (Center No.) (as assigned by Novartis to the investigative site) with a sequential patient number suffixed to it, so that each patient is numbered uniquely across the entire database. Upon signing the Molecular pre-screening Informed Consent Form or Informed Consent Form for the Study, the patient is assigned to the next sequential Subject No. available to the investigator through the Oracle Clinical RDC interface.

Once assigned, the Subject No. must not be reused for any other patient and the Subject No. for that individual must not be changed, even if the patient is re-screened.

6.4.2 Treatment assignment or randomization

The assignment of a patient to the treatment groups will be coordinated by Novartis. No randomization will be performed for this study.

6.5 Study drug preparation and dispensation

The investigator or responsible site personnel must instruct the patient or caregiver to take the study drug as per protocol. Study drug will be dispensed to the patient by authorized site personnel only. All dosages prescribed to the patient and all dose changes during the study must be recorded on the Dosage Administration Record eCRF.

BGJ398 will be provided by Novartis Pharma in hard gelatin capsules covering dosage strengths of 25 and 100 mg (expressed in mg of BGJ398 free base, open label bulk).

6.5.1 Study drug packaging and labeling

The study medication packaging has a 2-part label. Site personnel will add the patient number on the label. Immediately before dispensing the package to the patient, site personnel will detach the outer part of the label from the packaging and affix it to the source document (Drug Label Form) for that patient's unique patient number.

Medication labels will be in the local language and comply with the legal requirements of each country. They will include storage conditions for the drug but no information about the patient. Study drugs will be packed as open label supply which allows the patient to take medication at home.

6.5.2 Drug supply and storage

Study treatments must be received by designated personnel at the study site, handled and stored safely and properly, and kept in a secured location to which only the investigator and designated site personnel have access. Upon receipt, BGJ398 should be stored according to the instructions specified on the drug labels and in the [Investigator's Brochure].

6.5.3 Study drug compliance and accountability

6.5.3.1 Study drug compliance

Dosing data for BGJ398 will be recorded on the Dosage Administration eCRF.

Compliance will be assessed by the investigator and/or study personnel at each patient visit and information provided by the patient and/or caregiver will be captured in the Drug Accountability Form. This information must be captured in the source document at each patient visit.

6.5.3.2 Study drug accountability

The investigator or designee must maintain an accurate record of the shipment and dispensing of study treatment in a drug accountability log. Drug accountability will be noted by the field monitor during site visits and at the completion of the study. Patients will be asked to return all unused study treatment and packaging at the end of each cycle, at the end of the study or at the time of study treatment discontinuation.

At study close-out, and, as appropriate during the course of the study, the investigator will return all used and unused study treatment, packaging, drug labels, and a copy of the completed drug accountability log to the Novartis monitor or to the Novartis address provided in the investigator folder at each site.

6.5.3.3 Handling of other study treatment

Not applicable.

6.5.4 Disposal and destruction

The study drug supply can be destroyed at the local Novartis facility, Drug Supply group or third party, as appropriate

7 Visit schedule and assessments

7.1 Study flow and visit schedule

For all visits, there is a \pm 3-day window on assessments to take into account scheduling over public or religious holidays, **if not explicitly specified otherwise.** [REDACTED]

[REDACTED] For imaging assessments, a \pm 7 day window is allowed, except for the first post baseline assessment and for confirmatory scans (+7 day window only permitted). All screening assessments, including baseline imaging assessments, must be completed within 28 days before the first dose, with the exception of the serum pregnancy test (β -hCG) that needs to be performed \leq 72hrs before the first dose of study treatment. Every effort must be made to follow the schedule outlined in [Table 7-1](#).

[Table 7-1](#) lists all of the assessments and indicates with an “X”, the visits when they are performed. The table indicates which assessments produce data to be entered into the database (D) or remain in source documents only (S) (“Category” column).

Molecular pre-screening assessments can be performed any time prior to the initiation of screening.

Assessments which are indicated to be performed at screening and on Cycle 1 Day 1, need only to be repeated at Cycle 1 Day 1 if screening assessment was more than 3 days earlier.

[figure not shown]
All assessments should be performed as outlined in [Table 7-1](#) and as clinically indicated.

	Category	Reference to section	Molecular pre - screening	Screening	Pre-Surgical Treatment	Day of Surgery	Cycle 1					Cycle 2				Cycle 3	Subsequent cycles	End of study treatment	30 day Follow up	Disease Progression	Survival follow up			
			Screening Phase		Surgical phase (Group 2)			Treatment Phase													Follow-up			
Day of cycle				-28 to -1	1	5-10	6-11	1	2	8	15	22	1	8	15	22	1	22	1	22				
Relevant medical history/current medical conditions	D	7.1.2.3		X																				
Diagnosis and extent of cancer	D	7.1.2.3		X																				
Prior antineoplastic therapy	D	7.1.2.3		X																				
Prior/ concomitant medications	D	6.3		X	X	X	X	Continuous													X	X		
Antineoplastic therapies since discontinuation of study treatment	D	7.1.4																			X	X	X	X
Physical examination	S	7.2.2.1		X				X		X		X	X	X		X	X	X	X	X	X			
Height	D	7.2.2.3		X																				
Weight	D	7.2.2.3		X				X					X				X				X			
Vital signs	D	7.2.2.2		X				X		X	X	X	X	X	X	X	X	X	X	X	X			
Performance status	D	7.2.2.4		X				X				X	X			X	X		X		X			
Hematology	D	7.2.2.5.1		X				X					X				X		X		X			

	Category	Reference to section	Molecular pre - screening	Screening	Pre-Surgical Treatment	Day of Surgery	Cycle 1					Cycle 2				Cycle 3	Subsequent cycles	End of study treatment	30 day Follow up	Disease Progression	Survival follow up			
			Screening Phase		Surgical phase (Group 2)			Treatment Phase														Follow-up		
Day of cycle				-28 to -1	1	5-10	6-11	1	2	8	15	22	1	8	15	22	1	22	1	22				
Chemistry	D	7.2.2.5.2		X				X	X	X	X	X	X	X	X	X	X	X	X	X	X			
Coagulation	D	7.2.2.5		X				If clinically indicated																
Urinalysis (microscopic or macroscopic)	D	7.2.2.5.3		X				If clinically indicated																
Pregnancy test	D	7.2.2.5		X				X					X				X		X		X			
Ophthalmologic assessment	D	7.2.2.8		X				X			X		X				X		X		X			
Tumor response per RANO v1.0 (* : within 72 hours of surgery)	D	7.2.1		X			X*	First post baseline scan occurs cycle 3 day 1; subsequent scans occur every 8 weeks until unacceptable toxicity or disease progression, whichever occurs first														X		X
Surgery	D	4.1					X																	
Study drug administration		6.1			Continuous from day 1 till day of surgery			Continuous on a 3 weeks on 1 week off schedule																
12-Lead ECG (*pre-dose)	D	7.2.2.7		X	X*		X	X*					X*				X*		X*		X			

[figure not shown]

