Evidence of FGFR1-TACC1, FGFR3-TACC3 fusion and/or activating mutation in FGFR1, FGFR2, or FGFR3 is required in order to begin study screening. [REDACTED]

- If pre-screening data is not available at the time of study entry, the patient must sign the molecular pre-screening consent to allow for the collection and/or submission of samples to the Novartis designated laboratory for analysis.

If the local data or the results of the central analysis meet inclusion criteria ([Section 5.2](#)), the patient can proceed with the screening procedures.

Patients identified to have an activating mutation in FGFR1, 2 or 3 may be eligible pending agreement between Novartis and Investigator.

Screening

The screening period begins once the patient has signed the study informed consent. All screening evaluations are required to be performed before study treatment administration begins. Evaluations that were conducted prior to the signing of the informed consent document as a part of standard of care analysis may be used to demonstrate eligibility as long as the evaluations were conducted within allowed screening windows.

Treatment period

For patients in group 1 (non surgical group, unresectable disease), the treatment period will begin on cycle 1, day 1 and will continue until disease progression, unacceptable toxicity, withdrawal of informed consent, or death.

For patients in group 2 (surgical group, resectable disease), the treatment will begin 5-10 days prior to surgery with the last pre-surgical dose given within 24 hours of surgery. The duration of the treatment before surgery (5 to 10 days) will be left at the investigator discretion. Patients will be expected to resume the treatment upon surgical recovery (a minimum of 2 weeks and no more than 6 weeks post operatively, unless agreed otherwise between Novartis and the Investigator, on a case by case basis). The post surgical treatment will begin as cycle 1, day 1 and will continue until disease progression, unacceptable toxicity, withdrawal of informed consent, or death.

End of treatment

The EOT visit occurs within 14 days after last administration of study treatment ([Section 7.1.4](#)). All participating patients must complete this visit even if they have had to discontinue prematurely unless they are unable or unwilling to return.

Follow up

All patients will be followed up as described in [Section 7.1.5](#).

30-day safety follow-up period

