6.2 Dose modifications

6.2.1 Dose modification and dose delay

For patients who do not tolerate the protocol-specified dosing schedule, dose adjustments are permitted in order to allow the patient to continue the study treatment. These changes must be recorded on the Dosage Administration Record CRF.

All dose modifications should be based on the worst preceding toxicity. The following guidelines need to be applied:

Each patient will be allowed up to 2 dose reductions. Patients must discontinue BGJ398 if toxicities persist following 2 dose reductions ([Table 6-2](#)) unless a continuation is allowed in discussion with Novartis.

Following resolution of toxicity to baseline or \leq grade 1, treatment is resumed at either the same or lower doses of study drugs as per the criteria in [Table 6-3](#). If treatment is resumed at the same doses of study drugs, and the same toxicity recurs with the same or worse severity regardless of duration, doses must be reduced to the next lower dose level ([Table 6-2](#)). If treatment is resumed at the lower doses of study drugs, and the same toxicity recurs with the same or worse severity, the patient must discontinue study treatment unless a continuation is allowed in discussion with Novartis.

If a patient requires a dose delay of > 14 consecutive days of BGJ398 from the intended day of the next scheduled dose, then the patient should be discontinued from the study treatment unless a continuation is allowed in discussion with Novartis.

Patients who discontinue the study for a study related adverse event or an abnormal laboratory value must be followed as described in [Table 6-3](#) and [Section 6.2.2](#).

In exceptional situations, study treatment may continue even if the patient experienced one of the treatment stopping rules. The decision to allow for continuation of treatment will be made on a case-by-case basis following discussion between Novartis and the Investigator.

Situations that may allow for continuation of treatment include but are not limited to the following.

- A dose delay of > 14 days has occurred, but the patient is clearly benefiting from study treatment (i.e., stable disease, partial response, or complete response) and it is the investigator's opinion that no safety concerns are present, after discussion with Novartis Medical Monitor, the patient may remain on the study treatment

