7.1.2 Clinical Screening

The IRB/IEC study approved informed consent form (ICF) must be signed and dated before any screening procedure is performed. Procedures which are part of the clinical routine during the initial diagnostic work-up of the patient may be obtained before obtaining the ICF. A copy of the ICF must be given to the patient or to the person signing the form. The investigator or designee must record the date when the study informed consent was signed in the medical records of the patient.

Patients will be evaluated against study inclusion and exclusion criteria and safety assessments. For details of assessments, refer to [Table 7-1](#). Screening assessments must be completed within 28 days prior to the first dose of treatment with the exception of the serum pregnancy test (β -hCG) that needs to be performed ≤ 72 hrs before the first dose of study treatment. Clinical and radiological tumor assessment (RANO criteria) should be conducted preferably within 1 week (7 days) prior to the first dose of the study drug; however tumor assessments up to 4 weeks (28 days) prior to the first dose will be acceptable. Screening assessments must be repeated if >28 days from Cycle 1 Day 1.

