7.1.3 Treatment period

During the treatment period, the patient is obliged to follow the investigators instructions with regards to contraception, concomitant medications and dosing regimen. There is no fixed duration; patients may continue treatment with the study drug until the development of an unacceptable toxicity that precludes any further treatment, disease progression, and /or treatment is discontinued at the discretion of the Investigator or by patient refusal.

For the patients included in group 2 (surgical group), there is a fixed treatment duration of 5 to 10 days before surgery. The last dose should be on the day of surgery, or the day before at the discretion of the investigator. At a minimum of 2 weeks post-surgery, patients may resume study treatment with BGJ398 until experiencing unacceptable toxicity, disease progression and/or the treatment is discontinued at the discretion of the investigator or by patient refusal (withdrawal of consent). Day 1 of treatment following surgery will be considered to be Cycle 1 Day 1. For details of assessments during the treatment period, refer to [Table 7-1](#).

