7.2.2.5.2 Clinical chemistry

Clinical chemistry tests are to be performed by the local laboratory according to the Visit Schedule outlined in [Table 7-1](#). For details on the Biochemistry panel refer to [Table 7-3](#). Assessment of inorganic phosphorus will be performed as part of the chemistry analysis, or as indicated in [Table 7-1](#).

- On Cycle 1, Day 1, 8 hours post dose, inorganic phosphorous will be the only test conducted of the chemistry panel.
- On Cycle 1, Day 2, inorganic phosphorous will be the only test conducted of the chemistry panel.

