7.2.2.7 Cardiac assessments

7.2.2.7.1 Electrocardiogram (ECG)

A standard 12 lead ECG will be performed

- at screening
- pre-dose, on D1 of every cycle. For Cycle 1 Day 1 pre-dose ECG, the QTcF value must be within eligibility criteria prior to study drug treatment.
- Surgical group (group 2) : pre-dose on D1, and on the day of surgery
- at the EOT visit

[figure not shown]
A standard of 12-Lead ECG that monitors QTcF interval, heart rate, PR interval, uncorrected QT interval, and QRS duration will be performed as indicated in in [Table 7-1](#).

[figure not shown]
Interpretation of the tracing must be made by a qualified physician at the site and documented on the ECG eCRF. Each ECG tracing should be labeled with the study number, patient initials (where regulations permit), patient number, date, and kept in the source documents at the study site. Clinically significant abnormalities present when the patient signed informed consent should be reported on the Relevant Medical History/Current Medical Conditions eCRF. Clinically significant findings must be discussed with the Novartis Medical Monitor prior to enrolling the patient in the study. New or worsened clinically significant findings occurring after informed consent must be recorded on the AE eCRF.

[figure not shown]

[figure not shown]

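### In the visible schedule, Group 2 has no chemistry or hematology at its first BGJ398 dose, so laboratory values there can be up to 28 days old

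*Protocol*

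**What the plan says.** Group 2 takes BGJ398 for 5 to 10 days before resection. In Table 7-1 the study drug row for this phase reads "Continuous from day 1 till day of surgery". The restart comes 2 to 6 weeks after surgery. Protocol Section 4.1 says of it: "The post surgical treatment will begin as cycle 1, day 1". Section 7.1.3 agrees: "Day 1 of treatment following surgery will be considered to be Cycle 1 Day 1". So for operated Group 2 patients, Cycle 1 Day 1 is not the first exposure to the drug.

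Three protocol rules govern how recent the laboratory values must be:

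- Section 7.1 lets screening assessments, including imaging, be up to 28 days old at the first dose. Only the serum pregnancy test has a tighter limit (72 hours).
- Section 7.1 adds that assessments listed at both screening and Cycle 1 Day 1 "need only to be repeated at Cycle 1 Day 1 if screening assessment was more than 3 days earlier".
- Section 7.1.2 adds: "Screening assessments must be repeated if >28 days from Cycle 1 Day 1".

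The early phosphorus checks in Section 7.2.2.5.2 are also placed in Cycle 1 ("On Cycle 1, Day 1, 8 hours post dose, inorganic phosphorous will be the only test conducted of the chemistry panel", and again on Day 2). The ECG is handled differently: for Group 2, Section 7.2.2.7.1 places it "pre-dose on D1, and on the day of surgery".

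The SAP (Section 2.1.1) defines first administration as the first non-zero dose. Its non-efficacy baseline is the last valid value in the 21 days before that dose. Section 2.8.2 uses this baseline for the laboratory shift tables.

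**The concern.** The laboratory exclusion criteria in protocol Section 5.3 (marrow, hepatic and renal function, phosphorus, calcium) apply up to the first treatment. In Group 1 the three-day rule brings a panel close to that moment. In Group 2 the same rule attaches to the restart, after the patient has already had a course of drug and an operation. The protocol ties the pregnancy test and the ECG to the true first dose, and gives no reason for treating chemistry and hematology otherwise. This looks like an oversight in the table.

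Two things are at stake. A Group 2 patient may start a drug whose most frequent adverse event is raised phosphorus (74% in Section 1.2.1.2.1) on values nearly four weeks old. The same patient may also lack a pre-exposure laboratory baseline that the SAP's definition accepts, because the Cycle 1 Day 1 panel comes too late to serve as one.

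**Working it through.** **1. Is the blank real or an artifact of reading the table?** The rows were lined up against the day-of-cycle header.

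| Row | Screening | Pre-surgical Day 1 | Day 5-10 | Day of surgery (6-11) | Cycle 1 Day 1 |
|---|---|---|---|---|---|
| Chemistry | X | – | – | – | X |
| Hematology | X | – | – | – | X |
| ECG | X | X (pre-dose) | – | X | X (pre-dose) |

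The ECG row matches Section 7.2.2.7.1 exactly, which confirms the alignment. After the three blanks the chemistry row has 14 marks: Cycle 1 (5) + Cycle 2 (4) + Cycle 3 (2) + subsequent cycles (2) + end of treatment (1). All columns are accounted for.

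**2. Age of the laboratory values at first dose.** Screening runs from day -28 to day -1 and there is no day 0, so a sample on day -s is s days old on Day 1.

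- Group 2: s = 1 to 28, so the maximum is 28 days. This is the protocol's own screening limit.
- Group 1: if s > 3 the panel is repeated on Cycle 1 Day 1 (age 0); if s ≤ 3 it stands. The maximum is 3 days.

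**3. Where Cycle 1 Day 1 falls in Group 2.** Surgery is on day d = 6 to 11 and the restart is r = 14 to 42 days later, so Cycle 1 Day 1 is study day c = d + r.

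- Earliest: 6 + 14 = 20. Latest: 11 + 42 = 53.
- Time since first dose: 20 - 1 = 19 days to 53 - 1 = 52 days.

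These ranges ignore the ±3-day visit window and the agreed exceptions (earlier surgery, later restart).

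**4. Does the 28-day repeat rule close the gap?** The interval from screening to Cycle 1 Day 1 is s + c - 1, and a repeat is due when this exceeds 28.

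- At c = 20 a repeat is due only if s ≥ 10 (10 + 20 - 1 = 29).
- At c ≥ 29 a repeat is always due (even s = 1 gives 1 + 29 - 1 = 29).
- A repeat on study day x ≥ 1 complies if c - x ≤ 28, that is x ≥ c - 28. At c = 29 the earliest compliant day is Day 1 itself. For c = 30 to 53 it is Day 2 or later, after the first dose.
- For earlier restarts a compliant repeat may fall before or after the first dose, and the rule does not say which.

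The rule secures recent values for the restart. It requires none at the first dose.

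**5. SAP baseline.** The window covers s ≤ 21. Screening on days -28 to -22 (7 of the 28 permitted calendar days) lies outside it. The next scheduled panel, on study day 20 to 53, follows exposure. The seven days are calendar days, not a share of patients; the documents give no distribution of screening dates.

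**6. Size of the group.** With 34 patients and an expected 2:1 ratio, 34/3 ≈ 11 are in Group 2.

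**7. After the fix.** With the three-day rule tied to the first BGJ398 dose, a panel older than 3 days is repeated on pre-surgical Day 1. The maximum age falls from 28 days to 3, and every patient has a scheduled value inside the 21-day window.

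**The case against.** Several points on the other side stand.

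- **The schedule is only partly visible.** Section 7.1 has redacted text and figures are missing around Table 7-1. Section 7.2.2.5.2 describes an 8-hour phosphorus sample that no visible row shows. A phosphorus row or footnote for the surgical phase cannot be excluded. The legible chemistry and hematology rows are blank regardless.
- **Extra tests are allowed.** Section 7.2.2.5 permits additional laboratory work, and Section 7.1 calls for assessments when clinically indicated. Routine pre-operative bloods are likely too. None of these is required before the first dose.
- **The exposure is short.** Patients receive 5 to 10 days of drug with prophylactic phosphate binders. Section 2.3 gives a median of about 22 days to first interruption at 125 mg on continuous dosing.

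A reader might infer more than the documents support:

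- **That Group 1 is guaranteed a result before dosing.** The visible text schedules the panel at Cycle 1 Day 1 but does not say that it must be drawn or read before the dose. Only the ECG carries a pre-dose mark, and only QTcF must meet eligibility first. The contrast is a panel on the day or within 3 days before, against none.
- **That restart doses will be wrong.** Section 6.2.1 says "All dose modifications should be based on the worst preceding toxicity", and the visible table marks no on-drug chemistry during the pre-surgical doses. But the documents give no rate of laboratory toxicity over such a short course, and the restart has its own scheduled panel. They support no count of missed events.

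**Conclusion.** The point holds as a minor, cheap improvement. In the visible Table 7-1, Group 2 has no chemistry or hematology scheduled at its true first dose, and no repeat rule requires it there. Values can be 28 days old at that dose, against 3 in Group 1. A patient screened on days -28 to -22 could have no baseline for the laboratory shift tables. Those tables are descriptive, and the primary endpoint is not affected.

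This rests on three assumptions: that no redacted row or footnote fills the gap, that no discretionary test happens to be done, and that screening can fall anywhere in its permitted window. At most about 11 patients are concerned, and SAP Section 2.2 allows for there being none. The documents do not support a claim that patients would be harmed, or that a given share of them would lack a baseline.

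**What to change.** In protocol Section 7.1, tie the three-day repeat rule to *the first dose of BGJ398 (pre-surgical Day 1 in Group 2)*, and keep the existing repeat at Cycle 1 Day 1. In Table 7-1, add a pre-dose mark on pre-surgical Day 1 for chemistry (including phosphorus, calcium and creatinine) and for hematology. The visit already exists for the ECG. No dose or hold threshold changes, and the SAP needs no edit.

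The cost is one sentence, two table marks and at most one local draw per Group 2 patient (about 11 draws), waived when screening was within 3 days. Chemistry on the day of surgery and a vital-signs mark on pre-surgical Day 1 are optional extras and not part of this recommendation. The day-of-surgery result would have to be read before the operation and could delay it.
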